architectures can automatically identify morphological patterns related to CD8⁺ T cell infiltration density and PD-L1 expression, realizing cross-modal prediction of immune status based on H&E morphological features. Latest studies have verified that deep learning models based on H&E WSIs achieve high accuracy in predicting Microsatellite Instability (MSI) in colorectal cancer (AUC = 0.88), PD-L1 expression in non-small cell lung cancer (AUC = 0.80) and Tumor Mutation Burden (TMB) (AUC = 0.91). In the field of HCC, WSI-based deep learning models have also achieved favorable performance in predicting postoperative recurrence risk (AUC = 0.82) and immune cell infiltration (AUC = 0.78). However, no studies have focused on the critical clinical issue of predicting responses to postoperative adjuvant therapy (TACE/TKIs) by integrating preoperative imaging and postoperative multimodal pathological data, and large-scale multicenter prospective clinical validation is still lacking.

Accordingly, this study aims to integrate multicenter clinicopathological data with artificial intelligence algorithms to establish a multimodal predictive model based on preoperative imaging, postoperative pathological WSIs, pathological reports and clinical indicators. It intends to clarify the correlation between preoperative tumor characteristics and responses to postoperative adjuvant therapy, develop clinically applicable digital decision-making tools, and promote the multi-dimensional and full-cycle precise management of HCC.

Study Objectives

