(2) Construction and Multi-level Clinical Validation of Treatment Response Prediction Model

This is the core part of the study. Based on the quantified tumor immune microenvironment features output by the above model, combined with imaging data and essential clinical variables (such as TNM stage, Child-Pugh liver function classification and AFP level), a classification model will be built to predict patients' responses to four types of postoperative adjuvant therapy regimens: surgery alone, surgery combined with TACE, surgery combined with TACE plus systemic therapy, and surgery combined with systemic therapy alone. A strict hierarchical validation strategy will be adopted in this part.

Model Training Phase

Retrospective data from our center (n=1500) will be used. Inclusion criteria for patients in this phase: ① Histopathologically confirmed HCC; ② Underwent curative surgical resection; ③ Complete preoperative contrast-enhanced CT/MRI images, records of postoperative adjuvant therapy and follow-up data are available. Definition of treatment response: The primary endpoint is Relapse-Free Survival (RFS), and secondary endpoints include Overall Survival (OS) and Objective Response Rate (ORR). Multi-category machine learning algorithms (such as Gradient Boosting Decision Tree and Deep Neural Network) will be used for model training to output the most beneficial treatment regimen for each patient.

Internal Validation Phase

An independent validation set (n≈500, no overlap with the training set) will be randomly divided from the data of our center for preliminary evaluation of the model's discriminative performance and hyperparameter tuning to prevent overfitting.

External Validation Phase 1 (Retrospective Validation and Model Calibration)

Retrospective data (n=3000) will be collected from 8 to 10 medical centers nationwide. The main purposes of this phase are: ① To validate the model performance on larger and more heterogeneous external datasets; ② To calibrate or slightly optimize the model according to

validation results and finalize the predictive model.

External Validation Phase 2 (Large-scale Retrospective Validation)

The finalized model will be tested on a brand-new large-scale retrospective dataset (n=10,000) from 3 to 5 medical centers to further enhance the level of evidence and provide a solid basis for prospective studies.

(3) Study Population

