3.4.2 Sample Size for Prospective Study Phase

(1) Sample Size for Prospective Observational Validation ($n = 1,000$)

Estimation Basis: This phase evaluates the correlation strength between model predictions and real clinical prognosis (C-index) using sample size formulas for survival analysis. Relapse-Free Survival (RFS) is taken as the primary endpoint.

Assuming the 12-month RFS rate of the control group is 60% and the corresponding HR of the model-consistent group is 0.7, a total of 256 events are expected. Simulated by PASS 2021 software, more than 300 events can be observed in 1,000 cases within a 24-month study period (12 months for enrollment + 12 months for follow-up), which meets the requirements of statistical power and supports stratified analysis.

(2) Sample Size for Prospective Interventional Study

Estimation Basis: This phase is a Randomized Controlled Trial (RCT) with strictly calculated sample size, taking RFS as the primary endpoint.

Sample size formula for Log-Rank test is adopted with the following parameter settings: Baseline event rate: The 12-month RFS rate of the standard treatment group (Arm B) is 65%. Effect size: The 12-month RFS rate of the AI-assisted decision-making group (Arm A) is increased by an absolute value of 10% (up to 75%), corresponding to $HR = 0.67$. Significance level (α): 0.05. Statistical power ($1-\beta$): 80% (conventional standard for RCT). Accrual time: 18 months. Follow-up time: 12 months. Dropout rate: 10%.

Calculated by PASS 2021 software, a total of 200 events are required. Considering the dropout rate, the total required sample size is 600 cases (300 cases in each group). This sample size can detect the clinical difference corresponding to $HR = 0.67$ and meet the power requirements under follow-up and dropout conditions.

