Fairness assessment: Comprehensive fairness evaluation is carried out to analyze whether there are significant differences in model performance across subgroups divided by demographic characteristics (gender, age) and clinical characteristics (tumor stage, etiology, liver function classification). Core evaluation indicators include inter-group AUC difference, balanced odds and fairness metrics for sensitive attributes. If performance discrimination of the model is found in specific subgroups, algorithm correction will be performed to ensure the fairness of algorithm decisions. All fairness evaluation results will be fully disclosed in the research report.

Bias control in statistical analysis phase: Multivariate Cox regression model and Logistic regression model are used to adjust for known prognostic factors (such as TNM stage, vascular invasion and AFP level) to accurately estimate the independent predictive efficacy of the AI model and control potential residual confounding bias.

3.6 Data Governance System (Data Collection, Transmission, Storage Security Control; Full-chain Data Recording)

A sound data governance system is established to ensure the quality, security and compliance of data throughout the research process, covering all links including data collection, transmission, storage, processing, analysis and archiving, forming a complete data management closed loop.

Standardized data collection: Detailed Standard Operating Procedures (SOPs) for data collection are formulated to clarify the definition, format and collection specifications of all types of data. Structured electronic Case Report Forms (eCRFs) are used for clinical data collection with built-in logic verification and range check functions to ensure the accuracy and completeness of data collection. Pathological image data collection follows digital scanning standards with a unified scanning resolution of 0.25 μ m/pixel and file format of SVS. Equipment calibration and quality control tests are conducted before each batch of scanning. Laboratory test data are directly collected by docking with the Laboratory Information System (LIS) to avoid manual transcription errors.

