Data governance organizational structure: A data governance committee is set up to formulate data management policies. Dedicated data administrators are assigned to be responsible for daily data management. A data quality supervision team conducts regular data quality inspections. All researchers are required to receive and pass data management training to ensure the implementation of standardized data management.

3.7 Adverse Events (Specific Definition, Classification, Reporting Methods and Treatment Measures for Adverse Events/Serious Adverse Events)

Adverse events in this study refer to any negative medical outcomes related to AI-assisted decision-making, which are divided into three grades:

Grade 1 (Mild): AI recommendations lead to minor inconvenience or reversible additional examinations without long-term impacts;

Grade 2 (Moderate): AI recommendations result in inappropriate treatment regimens, which require medical intervention for correction without permanent damage;

Grade 3 (Severe): AI recommendations lead to misdiagnosis and mistreatment, causing permanent functional damage or significant shortening of survival time.

Once an adverse event occurs, the clinical center shall report it to the research safety monitoring committee through the online system within 24 hours. The committee consists of experts in hepatology, oncology, pathology and medical ethics. Treatment measures include immediately suspending the use of the AI system, organizing experts to assess the cause of the event, determining the correlation with the AI system, and formulating corrective measures. All adverse events will be fully recorded and included in the final research report.

3.8 Statistical Analysis Plan (Methods for Missing Data Processing, Definition and Selection of Statistical Analysis Datasets, Statistical Methods for Comparing Primary and Secondary Outcome Indicators, Algorithm Stability Evaluation)

R (Version 4.2.0), Python (Version 3.9) and SPSS (Version 26.0) software will be used for all statistical analyses. All statistical tests are two-sided with a significance level of $\alpha=0.05$.

Missing data processing: Multiple imputation method is adopted. For continuous variables, the Multiple Imputation by Chained Equations (MICE) is used to create 5 imputed datasets for combined analysis. Mode imputation is applied for categorical variables. The missing data mechanism will be tested: Complete Case Analysis is adopted for data Missing Completely at

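### The adjusted Cox/logistic regression and the C-index measure prognosis, so they cannot show that the AI model identifies the regimen a patient benefits from

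*Protocol*

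**What the plan says.** - **Task of the model.** Section 3.1, Part One (2), trains it "to output the most beneficial treatment regimen for each patient", choosing among surgery alone, surgery with TACE, surgery with TACE and systemic therapy, and surgery with systemic therapy.
- **Regression.** Section 3.5, in its paragraph on the statistical analysis phase, states that "Multivariate Cox regression model and Logistic regression model are used to adjust for known prognostic factors", giving TNM stage, vascular invasion and AFP as examples. The stated purpose is "to accurately estimate the independent predictive efficacy of the AI model".
- **C-index.** Section 3.4.2 (1) says of the observational phase: "This phase evaluates the correlation strength between model predictions and real clinical prognosis (C-index").
- **Size of that phase.** The same paragraph continues: "Assuming the 12-month RFS rate of the control group is 60% and the corresponding HR of the model-consistent group is 0.7", and "a total of 256 events are expected". It expects more than 300 events in 1,000 patients over 12 + 12 months.
- **Interactions.** The only interaction test named (section 3.8) covers age, gender, TNM stage and cirrhosis.
- **Other evidence on selection.** Section 3.1, Part Two, compares patients whose actual treatment did or did not match the model's choice. It also randomises 600 patients to AI-assisted or standard decision-making.

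**The concern.** A claim to name the most beneficial regimen is a claim about effect modification: the benefit of a regimen must differ according to what the model outputs. A regression of outcome on the AI output with prognostic covariates answers another question, namely whether patients with different outputs have different outcomes at the same stage, vascular invasion and AFP. The C-index asks much the same without the adjustment. A score that only sorts patients by recurrence risk does well on both, even if every regimen works equally well at every score.

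A purely prognostic output could therefore be reported as having independent predictive efficacy for adjuvant therapy. Slide and imaging features may well carry prognostic information: the Study Background cites existing slide-based models in HCC as "predicting postoperative recurrence risk (AUC = 0.82").

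**Working it through.** **1. What each analysis estimates.** Write A for the AI output, W for the regimen received and X for the prognostic factors.

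- As section 3.5 describes it: log hazard = baseline + βA + γX.
- What the section 3.1 claim needs: log hazard = baseline + βA + δW + θ(A×W) + γX.

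Selection value lies in θ. β can be far from zero when θ = 0. The C-index contains neither W nor θ.

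**2. The plan's own figure.** Inputs: HR 0.7 and two-sided 0.05 (sections 3.4.2 and 3.8). Power is not given for this phase, so 80% is assumed from the randomised trial. (1.960 + 0.842)² = 7.85 and (ln 0.7)² = 0.1272.

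- Freedman: 7.85 × (1.7/0.3)² = 253 after rounding up.
- Schoenfeld, 50:50 split: 4 × 7.85/0.1272 = 247. With a 40:60 split: 258.

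The stated 256 is reproduced to within about 3%. It belongs to the consistent/inconsistent contrast, not to the C-index or the section 3.5 regression.

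**3. How often a main effect is significant when θ = 0.** Success is taken as p<0.05, an assumption. Power = Φ(√(E(1−R²)) × ln HR − 1.96), where E is events, HR is the residual hazard ratio per SD of the output, and R² is its overlap with the covariates (assumed 0 to 0.5). Example: E = 300, R² = 0.5, HR 1.2 gives 12.25 × 0.1823 − 1.96 = 0.27, so 61%.

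The simulation column used 250 runs per row, n = 1,000, censoring uniform over 12-24 months, 12-month RFS 60%, four regimens, and the same treatment effect at every score. It produced about 480-525 events.

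| Residual HR per SD | Formula, 300 events | Simulation |
|---|---|---|
| 1.0 | 5% (nominal) | 6% |
| 1.1 | 21-38% | 41% |
| 1.2 | 61-88% | 96% |
| 1.3 | 90-99.5% | 100% |
| 1.5 | 99.9-100% | 100% |

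**4. C-index in the same runs.** Its lower 95% limit exceeded 0.5 in 92% of runs at residual HR 1.0, because the score was correlated with the clinical index. It exceeded 0.5 in 100% of runs at HR 1.1 and above.

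**5. Interaction in the same runs.** With regimens grouped into two, the regimen-by-score term was significant in 3-9% of runs (nominal 5%). It does not credit a purely prognostic score.

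**6. What the interaction needs.** For balanced halves, events = 16 × 7.85/(ln ratio)².

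- Ratio of HRs 0.5: 16 × 7.85/0.4805 = 262.
- Ratio of HRs 0.7: 16 × 7.85/0.1272 = 988.

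At a ratio of 0.7, power is Φ(√(300/16) × 0.3567 − 1.96) = 34% with 300 events and 50% with 480. At a ratio of 0.5 it is 85% and 97%.

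**The case against.** The case on the other side has four parts.

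- **Model terms belong to the statistical analysis plan.** Section 3.5 gives one sentence, an open covariate list, and no statement of how the AI output enters the model. That stands as far as missing detail goes. The point rests on what is stated: a named method is tied to a purpose it cannot serve, and the C-index sentence itself says prognosis.
- **Selection is examined elsewhere.** This stands. The consistent/inconsistent comparison uses the regimen received, and the trial randomises the use of the model. In the simulation above, the consistent/inconsistent comparison significantly favoured the useless model in only 0-2% of runs. It is not a clean test, however: it is non-randomised, it was significant in either direction in 3-54% of runs, and the result depends on the assumed regimen assignment.
- **The prognostic null may be true.** A reader might infer from the cited AUC of 0.82 that it is false before the study starts. The documents do not support that. The figure comes from other models, trained on recurrence, with no adjustment stated, whereas section 3.5 concerns information beyond the covariates.
- **The interaction is weak evidence too.** This stands for moderate effects, as step 6 shows, and four regimens by four recommendations give 3 × 3 = 9 interaction terms with sparse cells likely.

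**Conclusion.** The point holds for the section 3.5 regression and the section 3.4.2 C-index, and no further. As described, both measure association with prognosis, and neither can show that the recommended regimen is the one that benefits the patient. With p<0.05 as the assumed criterion and about 300-500 events, an output with no selection value would appear independently predictive in about 61-96% of studies at a residual HR of 1.2 per SD and 90-100% at 1.3 or more. At HR 1.1 the figure is about 21-41%, and with nothing added beyond the covariates about 6%. The residual HR is unknown, so these are conditional rates.

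Stronger readings are tempting but unsupported:

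- **That a useless model passes almost surely and enters the randomised trial on that basis.** The protocol sets no threshold or go/no-go rule for either analysis. Section 3.1 names the second external validation set as the groundwork for the prospective studies.
- **That the programme never tests treatment selection.** The consistent/inconsistent comparison and the randomised trial both address it.
- **That the regression would miss a model that truly selects treatment.** This can be produced with assumed opposing effects (HR 0.6 if recommended, 1.2 if not) and moderate prognostic content, but the documents give no such figures.

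**What to change.** 1. In sections 3.5 and 3.4.2, label the adjusted main effect of the AI output and the C-index as prognostic performance.
2. For predictive efficacy, add to the section 3.5 model the regimen received and its interaction with the AI recommendation. Keep the same prognostic adjustment and add propensity weighting for regimen choice.
3. Report the interaction, that is, the regimen effect in patients recommended that regimen against those not recommended it, with its 95% CI.
4. State that this analysis supports, and does not replace, the consistent/inconsistent comparison and the randomised trial.

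**Cost.** No new data are needed, since the inclusion criteria already require regimen and medication records. The work is a change of wording, one set of model terms and a propensity model. The price is precision: the estimate is non-randomised, sparse for the rarer regimens, and at the planned events adequate for a ratio of HRs near 0.5 but not for 0.7. The protocol should say so, because the reported evidence may look weaker than a main effect would.

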The study population consists of patients who underwent curative surgical resection for HCC. Multiple datasets will be established for model development, training and validation, and all datasets will be constructed in accordance with strict inclusion and exclusion criteria.

(1) Patient Inclusion and Exclusion Criteria

Inclusion Criteria

Histopathologically confirmed diagnosis of hepatocellular carcinoma;

Aged between 18 and 75 years old;

Underwent curative resection (R0 resection) for primary hepatocellular carcinoma;

Complete postoperative formalin-fixed paraffin-embedded (FFPE) H&E-stained tissue slides eligible for digital scanning;

Complete and accessible clinicopathological data and follow-up data, including but not limited to age, gender, HBsAg status, liver cirrhosis background, AFP and PIVKA-II levels, tumor size and number, CNLC stage, AJCC 8th TNM stage, BCLC stage, vascular invasion status, tumor differentiation grade, detailed postoperative adjuvant therapy regimens and medication records, as well as postoperative tumor recurrence and survival data;

Preoperative contrast-enhanced CT or MRI images with standardized scanning parameters and no severe artifacts, meeting the requirements for analytical use.

Exclusion Criteria

Received anti-tumor treatments such as TACE, targeted therapy, immunotherapy and radiotherapy at non-collaborative medical centers before surgery, with unavailable original imaging and clinical baseline data;

Combined with primary malignant tumors of other organs;

Positive surgical margins after surgery (R1 or R2 resection);

Poor quality of pathological tissue slides (such as severe fading, folding, breakage or insufficient tissue volume), which cannot be used for digital scanning or reliable analysis;

Severe missing of clinical or follow-up data;

Missing preoperative imaging data or unqualified imaging quality (such as severe artifacts or incomplete scanning sequences) that cannot be used for analysis.

(2) Definition and Source of Datasets

A multi-center and multi-stage data collection strategy will be adopted for all datasets, which are strictly divided according to purposes to ensure mutual independence of the training set, validation set and test set and avoid data leakage.

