3.3 Evaluation Index System (Algorithm Performance, Clinical Utility, System Stability)

This study comprehensively evaluates the overall value of the AI model from three dimensions: algorithm performance, clinical utility and system stability.

Evaluation of Algorithm Performance

Conducted mainly during model development and validation, quantitative indicators are used to objectively assess the accuracy and robustness of the tumor immune microenvironment identification model and treatment response prediction model.

For the tumor immune microenvironment identification model: At the pixel level, Dice Similarity Coefficient (DSC) is used to evaluate the coincidence degree between segmentation results and expert annotations, and Intersection over Union (IoU) is adopted as a supplementary indicator. At the regional level, Precision, Recall and F1-Score are used to evaluate the recognition performance of specific components in the immune microenvironment.

For the treatment response prediction model: Area Under the Receiver Operating Characteristic Curve (AUC-ROC) is used to evaluate the binary classification ability of the model, and macro-average and micro-average AUC values are calculated. Accuracy, Precision, Recall and F1-Score calculated based on the confusion matrix are used to evaluate the performance of multi-classification tasks. Calibration Curve and Brier Score are used to assess the accuracy of predicted probabilities.

Evaluation of Clinical Utility

Conducted in the prospective study phase, focusing on evaluating the actual impact of the model on clinical decision-making and patient prognosis.

Primary clinical endpoints: Relapse-Free Survival (RFS), defined as the time from randomization to tumor recurrence or death from any cause. The Kaplan-Meier method is used for survival analysis, the Log-rank test is adopted for inter-group comparison, and the Hazard Ratio (HR) and its 95% confidence interval are calculated. Overall Survival (OS), defined as the time from randomization to death from any cause, is analyzed using the same statistical methods.

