Random (MCAR); multiple imputation is used for data Missing at Random (MAR); selection models are applied for data Missing Not at Random (MNAR). Sensitivity analysis is conducted to compare results obtained by different missing data processing methods.

Definition of statistical analysis datasets:

Full Analysis Set (FAS): Includes all randomized patients who received at least one efficacy assessment, analyzed according to the Intention-To-Treat (ITT) principle.

Per-Protocol Set (PPS): Includes patients who fully complied with the research protocol, excluding patients with major protocol violations.

Safety Set (SS): Includes all patients who received at least one treatment, used for safety evaluation.

Primary analysis is based on the FAS, and the PPS is used for sensitivity analysis to verify the robustness of results.

Statistical methods for primary outcome indicators: For categorical variables (such as treatment response grouping), weighted F1-score and macro-average AUC are taken as main evaluation indicators, and Cohen's Kappa coefficient is used to assess the consistency between model predictions and actual clinical conditions. For survival data (RFS and OS), the Kaplan-Meier method is used to draw survival curves, the Log-rank test is used for inter-group comparison, and the Cox proportional hazards regression model is established to calculate the Hazard Ratio (HR) and its 95% confidence interval while adjusting for potential confounding factors such as age, gender and TNM stage.

Statistical methods for secondary outcome indicators: Decision Curve Analysis (DCA) is used to evaluate the clinical net benefit of the model. Calibration Curve and Brier Score are used to assess the accuracy of predicted probabilities. Repeated-measures Analysis of Variance is used for inter-group comparison of continuous variables. The Mann-Whitney U test is adopted for ordinal variables such as physician adherence and decision confidence scale scores.

Algorithm stability evaluation: Bootstrap sampling (1,000 repetitions) is used to calculate the 95% confidence interval of model performance indicators for stability assessment. SHapley Additive exPlanations (SHAP) values are used to analyze feature importance and improve model interpretability. Intraclass Correlation Coefficient (ICC) is calculated to evaluate the consistency of the model across different centers; $ICC > 0.75$ is regarded as good consistency.

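### F1, macro-AUC and kappa cannot validate a best-of-four-regimens recommendation, because the best regimen is never observed and no rule derives it from RFS; ORR also has no measurable tumour to act on after R0 resection

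*Protocol*

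**What the plan says.** **Target.** Protocol section 3.1, Part One (2), builds a classification model over four regimens: "surgery alone, surgery combined with TACE, surgery combined with TACE plus systemic therapy, and surgery combined with systemic therapy alone". It is trained on retrospective records of the adjuvant therapy each patient had, "to output the most beneficial treatment regimen for each patient". Section 3.4.1 also counts four categories.

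**Definition of response.** The same part of 3.1 defines treatment response by endpoints only. RFS is primary, and "secondary endpoints include Overall Survival (OS) and Objective Response Rate (ORR". No rule turns any of these into a class for a patient.

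**Metrics.** In 3.3, accuracy, precision, recall and F1 "calculated based on the confusion matrix are used to evaluate the performance of multi-classification tasks", and AUC-ROC is described as measuring binary classification. In 3.8, for categorical outcomes such as response grouping, "weighted F1-score and macro-average AUC are taken as main evaluation indicators". A kappa statistic is added there as a third measure, "used to assess the consistency between model predictions and actual clinical conditions".

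**Population.** Eligible patients "Underwent curative resection (R0 resection) for primary hepatocellular carcinoma"; R1 and R2 resections are excluded.

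**The concern.** A confusion matrix, F1, multi-class AUC and kappa all compare a predicted class with a true class. When the prediction is the best of four regimens, the true class is a comparison of four outcomes, three of which never occur. A metric that needs this class must borrow another one, and then it answers another question.

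This matters because 3.1 presents the large retrospective validation as the basis for the prospective studies. The external sets hold 3,000 + 10,000 = 13,000 patients, and 3.4.1 sizes the larger one on an AUC of 0.80 without saying which outcome that AUC discriminates. A high score could be taken as evidence that the recommendations are good when it measured something else. A model that chooses well could also score badly. In the randomised trial (3.1, Part Two), physicians in the intervention group then plan treatment with reference to the model's output.

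**Working it through.** The plan states no figure on this point to reproduce. The check is one of logic, with an illustration.

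**Step 1: which reference class could be used?** The text leaves two candidates.

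- *Reading A: the regimen given.* It is the only regimen class on record. Kappa against clinical conditions (3.8) and the grouping of observational patients by model–physician agreement (3.1, Part Two) are compatible with it, but neither states it.
- *Reading B: response under the regimen received.* The mention of response grouping in 3.8 and of binary classification in 3.3 point this way.

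**Step 2: Reading A.** Inputs from 3.4.2: 12-month RFS 60%, HR 0.7. These are borrowed here to mean that a patient on the truly best regimen has HR 0.7 against any other. That use is an assumption.

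- 12-month RFS on the best regimen: 0.60^0.7 = 0.699.
- Let p be the share of patients whose physicians already gave the best regimen. RFS under practice = 0.600 + 0.0994p. Gain from a perfect model = 0.0994(1 − p). Accuracy of that perfect model against the regimen given = p.

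| p (assumed) | RFS in practice | Accuracy of perfect model vs regimen given | RFS gain if followed |
|---|---|---|---|
| 0.25 | 0.625 | 0.25 | 7.5 points |
| 0.50 | 0.650 | 0.50 | 5.0 points |
| 0.75 | 0.675 | 0.75 | 2.5 points |
| 1.00 | 0.699 | 1.00 | 0 |

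An exact copy of physicians has accuracy 1 and gain 0 in every row. Wherever there is anything to gain, the copy outscores the perfect model.

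A simulation of 10,000 patients gives the other metrics for p near 0.25. It assumes the best regimen is uniform over four classes and that physician choice is unrelated to it. All metrics are scored against the regimen received.

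| Model | Weighted F1 | Kappa | Macro-AUC | 12-month RFS if followed |
|---|---|---|---|---|
| Imitates physicians | 0.685 | 0.58 | 0.895 | 62.5% |
| Perfect best-regimen | 0.249 | −0.001 | 0.499 | 69.9% |
| Physician practice | – | – | – | 62.5% |

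Taking labels only from relapse-free patients does not repair this. The share of them who received their best regimen is 0.25 × 0.699 / 0.625 = 28.0%, and the simulation also gives 28.0%, against 24.9% of all patients.

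**Step 3: Reading B.** Response under the received regimen is observable, so the metrics can be computed. They then show whether the model separates patients who relapse from those who do not. A model that uses only stage and AFP and ignores the regimen can do that well while saying nothing about which regimen suits whom. RFS is also a censored time. A binary AUC needs a horizon and a way to treat patients censored before it, and neither is given.

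**Step 4: adjustment.** Section 3.5 adjusts for prognostic factors to isolate the model's predictive efficacy, and 3.8 adjusts the Cox model for factors such as age, gender and TNM stage. No method for estimating the comparative effect of the four regimens is named.

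**Step 5: ORR.** Eligibility requires R0 resection and excludes R1/R2, and one of the four classes is surgery alone. There is no measurable tumour when adjuvant therapy starts, no measurable-disease subset, and no other definition of ORR. Response of a later recurrence would be a different endpoint, which is not described. Sections 3.3 and 3.8 contain no analysis that uses ORR.

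**The case against.** The strongest defence is that the plan does not rest on agreement with physicians.

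- A reader might infer that F1, AUC and kappa can be computed only against the regimen given and so measure nothing but imitation. The documents do not support that. Section 3.8 speaks of response grouping, its kappa refers to clinical conditions rather than decisions, and the observational phase aims to compare predictions with actual outcomes. This stands, and it is why Reading B is examined too. Reading B still does not test the choice of regimen.
- Outcome-based checks are already planned: a C-index and an RFS comparison of consistent and inconsistent patients (3.1, 3.4.2), and calibration, Brier score and decision curves (3.3, 3.8). This stands in part. The consistent-versus-inconsistent comparison covers 1,000 non-randomised patients and has no treatment weighting. The C-index appears in 3.4.2 but not in 3.3 or 3.8. Calibration, Brier score and decision curves share the difficulty if they use the same undefined label. No comparison of recommended with actual care is described for the 13,000 external patients.
- The simulation builds in its result by scoring against the regimen given and making physician choice unrelated to the best regimen. This is fair. It shows what can happen, not how often; the first table shows the gap shrinking as p rises.
- Horizon, censoring and label coding are usual SAP detail. That is reasonable for the coding alone. But 3.8 already fixes the main metrics, and no coding makes the best of four regimens observable.
- ORR is named once and feeds no stated analysis. True, so removing it is a small correction.

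**Conclusion.** The point holds for model training and for the retrospective and observational validation. The main indicators named in 3.8 need a true best-regimen class that is never observed and that the protocol does not derive from RFS. On one permitted reading they reward agreement with physicians; on the other they measure prognosis and treat a censored time as binary. Neither validates the recommendation.

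A reader might go further and infer that the randomised trial is compromised, or that the validation programme would show nothing. The documents do not support either. The trial compares RFS between randomised groups and does not depend on any class label, and the planned survival comparisons carry some information.

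The size cannot be fixed from the documents. The illustrative gap of 69.9% − 62.5% = 7.4 points in 12-month RFS, with the ranking by F1 reversed (0.249 against 0.685), rests on the borrowed 60% and HR 0.7, on scoring against the regimen given, and on physician choice being unrelated to the best regimen. The logical point needs none of these. The ORR point rests only on the eligibility criteria.

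**What to change.** For the response model, replace weighted F1, macro-AUC and kappa as main indicators with two analyses.

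1. **Prediction within each received regimen.** Compare predicted with observed RFS using C-index, calibration, and time-dependent AUC and Brier score with censoring weights. Use 12 months in all sets, and 24 months only in retrospective sets with enough follow-up. With 12 months' enrolment plus 12 months' follow-up (3.4.2), observational patients have 12 to 24 months at close, and only the first enrolled reach 24.
2. **Value of the recommendation.** Estimate RFS under the recommended regimen versus actual care by treatment weighting or a doubly robust method, adjusting for stage, vascular invasion, AFP, Child-Pugh and centre. Do this in the external retrospective sets, and apply the same adjustment to the planned consistent-versus-inconsistent comparison. Label the result as relying on measured confounders.

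Report agreement with physicians as descriptive only. Remove ORR from the definition of treatment response. Settle these changes before the locked model is run on the 10,000-patient set.

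**Cost.** Extra analysis on data the protocol already plans to collect; most are not yet in hand (400 of the 1,500 centre cases so far). The second analysis stays open to unmeasured confounding.
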